1.3. Benefit and Risk Assessment

Etrasimod has been found to be safe and well-tolerated in approximately 281 subjects that have been dosed with the investigational drug. [REDACTED]

[REDACTED]

Etrasimod has already demonstrated beneficial effects in another autoimmune inflammatory disease, UC, in a Phase 2 study (Study APD334-003) with 1 and 2 mg etrasimod dosed once daily and the Open-Label Extension (Study APD334-005) with an etrasimod 2 mg dose administered once daily for up to 46 weeks.

There have been no clinically significant safety concerns in clinical studies with etrasimod to date. However, macular edema, liver enzyme elevations, and dyspnea have been reported with fingolimod, one of the currently licensed S1P receptor modulators (GILENYA 2010). It is believed that the non-selectivity (ie, activity at all 5 S1P receptors) of this first-generation S1P receptor modulator contributes to many of these adverse events (AEs) (Peyrin-Biroulet 2017). Given the putative association between receptor activation and AEs, development of etrasimod, as a next-generation S1P receptor modulator, has focused on optimizing selectivity for those receptors associated with clinical benefit (S1P_{1,4,5}) and avoidance of the receptors that initiate downstream signaling events believed to be connected to AEs (S1P_{2,3}).

[REDACTED]

The S1P receptor modulator class of drugs are also associated with an expected, on-target effect of reducing heart rate (HR) upon first dosing. This chronotropic reaction is caused by agonism of S1P₁ in cardiac tissue, which activates G protein-coupled inwardly rectifying potassium channels. S1P₁-mediated HR reduction is maximal on the first day of dosing, with recovery thereafter (Camm 2014). Cardiac events have been rare, asymptomatic, and transient with etrasimod.

[REDACTED]

Vital signs will be monitored closely during the study and direct observation will be performed during the period after the subject receives the Day 1 dose in the Double-Blind and Open-Label Extension periods and also at treatment re-initiation after a defined period of treatment interruption.

Based on the preclinical and clinical data generated from etrasimod studies along with the precautions outlined above, the favorable benefit/risk assessment justifies the further development of etrasimod in subjects with AD with this Phase 2 study.

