11.9. Statistical Considerations for the Open-Label Extension Period

The objectives of the Open-Label Extension Period are to evaluate long-term safety, tolerability, and efficacy up to 52 weeks for eligible subjects who complete the 12-week Double-Blind Treatment Period and the Safety Follow-Up Visit 4 weeks after last dose of study treatment. All subjects will receive 2 mg etrasimod treatment during Open-Label Extension Period.

No pair-wise comparison will be performed. Only descriptive statistics will be provided and details will be discussed in the SAP.

Analysis sets: all safety outcomes will be analyzed in Safety Set which includes all subjects who receive at least 1 dose of etrasimod. Efficacy outcomes will be summarized in efficacy evaluable set which includes subjects who receive at least 1 dose of etrasimod and have at least 1 efficacy measurement during the Open-Label Extension Period; therefore, efficacy evaluable set is endpoint specific.

Baseline for the Open-Label Extension Period is defined as the last measurement prior to the first etrasimod dose started at Week 16.

Safety analyses will follow general considerations in Sections 11.8.1 to 11.8.7 with following exceptions:

- 1 treatment group in the Open-Label Extension Period and 3 subgroups in the Double-Blind Treatment Period will be analyzed
- the Open-Label Extension Period visits will follow [Table 9](#) in [Appendix 1](#)

- change from baseline will be analyzed on change from Double-Blind Treatment Period baseline, and change from Open-Label Extension Period baseline, respectively

Efficacy outcomes will be measured at scheduled visits in the Open-Label Extension Period: EASI, vIGA, SCORAD, BSA, Pruritus NRS, POEM, DLQI, and PGA (Table 9 of Appendix 1). Dichotomous response outcomes derived from specific scores will be assessed. Continuous variables will be summarized by visit using the number of observations, mean, SD, median, minimum, and maximum; and categorical variables will be summarized by visit using frequency counts and percentages, with following considerations.

- 1 treatment group in the Open-Label Extension Period and 3 subgroups in the Double-Blind Treatment Period will be analyzed
- change from baseline in continuous variables will be analyzed on change from Double-Blind Treatment Period baseline, and change from Open-Label Extension Period baseline, respectively

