Statistical analysis will be performed following IQVIA Biotech standard operating procedures and on the IQVIA Biotech computer network. All statistical analysis will be performed using SAS Version 9.4 with program code prepared specifically for the project by qualified IQVIA Biotech statisticians and SAS programmers.

All observed and derived variables (e.g., change from baseline, percentage change from baseline, and response status) that are analyzed or summarized will be listed by subject. Descriptive statistics will provide an overview of the efficacy and safety results. For categorical parameters, the number and percentage of subjects in each category will be presented. For continuous parameters, descriptive statistics will include number of subjects, mean, SD median, minimum, and maximum.

B. Definition of Baseline and Study Day

Study day will be defined separately for the DB Treatment Period and OLE Period. For all subjects, Day 1 is the date of first study drug administration in the DB Treatment Period. This will be referred to as the **Overall Day 1**. For those enrolling into the OLE Period, an **OLE Day 1** will be additionally defined as the date of the first study drug administration in the OLE Period at Week 16.

Study day will be calculated relative to the date of Overall Day 1.

Similarly, Baseline will be defined separately for DB Treatment Period and OLE Period as follows:

[figure not shown]
- **DB Treatment Period:** baseline will be defined as the last available measurement prior to the first dose of the study drug in DB Treatment Period. Specifically, for vital signs (resting heart rate (HR), blood pressure (BP), body temperature, and respiratory rate) and [REDACTED], the Day 1 pre-randomization assessments will be used as baseline measurements. The lowest pre-dose HR measurement will be used for comparison to the post-dose HR measurement. This will be referred to as the **DB baseline**.

[figure not shown]
- OLE Period: for those enrolling into the OLE Period, an **OLE baseline** will be additionally defined as the last pre-dose measurement at Week 16 at Week 16.

Change from baseline is defined for both DB Treatment Period and OLE Period as the post-baseline value minus the baseline value unless otherwise specified. Percent change from baseline is calculated as follows: Percent change = (Change from baseline / Baseline) x 100.

C. Analysis Visit Window

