Individual subject plasma concentrations will be plotted (in both linear and semilogarithmic scales) versus actual time from start of treatment, for timepoints in DB Treatment Period (Baseline/Day 1 to Week 16) and for timelines in OLE Period (Week 16 to 72), separately.

C. Steady-State (SS) Concentration Analysis

Steady-state (SS) concentration will be assessed for the DB Treatment Period and OLE Period separately. Individual subject SS pre-dose (trough) plasma concentrations will be averaged across ($C_{ss,avg\ trough}$) across the timeframe shown by the statistical model to be steady state; for the DB portion, out to a maximum timeframe of 12 weeks, and in the OLE out to a maximum of 68 weeks. Only C_{trough} values in the range of steady state will be averaged into $C_{ss,avg, trough}$. Individual SS pre-dose concentrations will be included in the data listings and summarized using descriptive statistics as described above for DB Treatment Period and for OLE Period separately (except with respect to scheduled nominal time which is not applicable).

Box plots of SS pre-dose (trough) plasma concentrations will be plotted versus scheduled nominal time for each scheduled nominal visit, by treatment received in DB Treatment Period and overall.

Box plot of $C_{ss,avg\ trough}$ will be plotted by treatment received in DB Treatment Period and overall.

Scatter plot matrices, stratified by treatment, of individual subject $C_{ss,avg\ trough}$ values versus baseline body weight and age will also be plotted, and showing correlation coefficient (Spearman's rank correlation coefficient) and p-value.

Etrasimod plasma steady-state will be determined by regressing trough (pre-dose) concentration values over time for the DB Treatment Period (Baseline/Day 1 to Week 16) and OLE Period (Week 16 to Week 72) separately and the resultant slope will be tested for its difference from zero. For each treatment period, a set of data ranged by weeks will be fitted using a mixed effect model with Treatment group (for DB Treatment Period) and week (as a continuous covariate) as fixed effect terms and subject as a random effect term. Steady state is estimated to be achieved as the earliest week included in the analysis when the 90% CI of the slope includes 0.

D. Exposure-Response Relationship Analysis

To explore potential etrasimod plasma exposure-response relationships, the following will be generated, and Baseline below refers to DB Baseline:

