- Scatter plot matrix of individual subject change from baseline in EASI Score at Week 12 values versus corresponding individual subject pre-dose (trough) concentrations at Week 12, and showing correlation coefficient r - and p-value (Spearman's rank correlation coefficient). The same approach will also be used to generate another set of similar scatter plots but using instead

individual subject $C_{ss,avg}$ trough concentrations (rather than Week 12 predose concentrations).

█ [REDACTED]

█ [REDACTED]

- Overlay plot showing profiles of mean (SD) heart rate absolute change from baseline (first dose cardiac monitoring) and mean (SD) plasma concentration versus scheduled nominal time from start of treatment for Day 1 will be plotted by DB treatment. A similar set of overlay plots will also be generated instead using mean (SD) heart rate (beats/min) and mean (SD) heart rate percent change from baseline values (ECG data).
- Overlay plot showing profiles of mean (SD) heart rate absolute change from baseline (first dose cardiac monitoring) and mean (SD) plasma concentration versus scheduled nominal time from start of treatment for Week 16 will be plotted by DB treatment. A similar set of overlay plots will also be generated instead using mean (SD) heart rate (beats/min) and mean (SD) heart rate percent change from baseline values (ECG data).
- A scatterplot of individual heart rate versus individual etrasimod plasma concentration from start of treatment for Day 1 and all scheduled nominal time by DB treatment, depicting regression relationship, will be generated; treatment groups will be denoted using different symbols but a single regression presented.

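### The Week 16 plots of heart-rate change in SAP Appendix 1.D would be computed from the Day 1 baseline, so they mix the acute Week 16 effect with the pre-dose difference between the two visits

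*SAP*

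**What the plan says.** SAP Appendix 1.D (Exposure-Response Relationship Analysis) introduces its list of outputs with one rule: "the following will be generated, and Baseline below refers to DB Baseline". One item in the list overlays mean absolute change in heart rate, from first-dose cardiac monitoring, on mean plasma concentration, "versus scheduled nominal time from start of treatment for Week 16 will be plotted by DB treatment". The same item adds companion plots: "A similar set of overlay plots will also be generated instead using mean (SD) heart rate (beats/min"), and mean percent change from baseline using ECG data. Nothing in the visible text exempts the Week 16 item from the opening rule.

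SAP 5.B defines two baselines. For the double-blind period, "baseline will be defined as the last available measurement prior to the first dose of the study drug in DB Treatment Period". For heart rate it points to the Day 1 assessments before randomization and takes the lowest pre-dose reading as the comparator for post-dose values. For subjects who enter the extension, an OLE baseline is "additionally defined as the last pre-dose measurement at Week 16". Protocol 11.9 agrees: the extension baseline is "defined as the last measurement prior to the first etrasimod dose started at Week 16". It asks for extension safety data as change from each of the two baselines.

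SAP 9.E does so for vital signs in the extension. It also presents pre-dose values, and change after treatment initiation, at both baseline and Week 16.

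**The concern.** A first-dose heart-rate plot should show how heart rate moves after the dose as concentration rises. Protocol 1.3 says of the drug class that "HR reduction is maximal on the first day of dosing", with recovery afterwards, so the relevant reference is the reading just before that dose. Week 16 is a first-dose occasion in its own right. Former placebo subjects take etrasimod for the first time, former etrasimod subjects restart after 4 weeks off drug, and Protocol 9.2.5 repeats cardiac monitoring.

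With the Day 1 reference, the curve also carries whatever separated the two visits: change in disease state, season, time of day or ordinary variation in resting heart rate. The curves are drawn by double-blind arm. A between-visit difference that varies by arm would therefore blur the comparison of first exposure with re-exposure. At stake is how a few exploratory safety displays are read. No efficacy result depends on them.

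**Working it through.** The plan states no figure on this point to reproduce. The check compares the definitions and then applies an identity.

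**1. Which baseline applies.** The opening rule of Appendix 1.D covers every item below it. The Week 16 absolute-change and percent-change plots need a baseline, so they take the Day 1 value. The raw beats/min plot needs none. The OLE baseline of SAP 5.B exists and is used in SAP 9.E, but it is not carried into Appendix 1.D.

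**2. Whether Week 16 is a new first dose for former etrasimod subjects.** Protocol 9.2.4 puts Week 16 four weeks after the last double-blind dose. Protocol 10.5.7.3 gives a half-life of about 33 hours. Time off drug = 28 × 24 = 672 h, and 672 / 33 = 20.4 half-lives. The fraction remaining is 0.5^20.4, about 7 × 10^-7. Drug carried over from the double-blind period is negligible.

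**3. What is plotted.** For a subject at time t after the Week 16 dose:

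HR(t) − HR(Day 1) = [HR(t) − HR(Week 16 pre-dose)] + [HR(Week 16 pre-dose) − HR(Day 1)]

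The first bracket is the acute effect. The second is the between-visit difference, and it does not depend on t. With the same subjects at each time point, it moves the absolute-change curve up or down as a whole.

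Illustration with assumed values: if the acute change is −8 bpm and the mean between-visit difference runs from −5 to +5 bpm, the curve reaches −8 − 5 = −13 to −8 + 5 = −3 bpm. Its pre-dose point sits at −5 to +5 bpm instead of zero.

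**4. Size of the shift by chance.** The SD of the between-visit difference and the number per former arm are not in the documents. I assume SD 6 to 10 bpm and n = 20 to 30, out of 40 planned per arm. With no true drift, the 95% range of the mean shift is ±1.96 × SD/√n:

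- SD 6, n = 30: 1.96 × 6/√30 = 2.15 bpm
- SD 8, n = 30: 1.96 × 8/√30 = 2.86 bpm
- SD 10, n = 20: 1.96 × 10/√20 = 4.38 bpm

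Any true mean drift adds to this in full.

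**5. Effect on the plotted SD.** With equal variances, the SD of a change is SD × √(2(1 − ρ)). Assume a heart-rate SD of 10 bpm:

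- From the Week 16 pre-dose value, within-visit ρ = 0.85: 10 × √0.30 = 5.5 bpm
- From Day 1, between-visit ρ = 0.8: 10 × √0.40 = 6.3 bpm
- From Day 1, between-visit ρ = 0.4: 10 × √1.20 = 11.0 bpm

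The SD is wider whenever readings on different visits correlate less than readings on the same visit, which is the usual case.

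The variances of the two brackets in step 3 cannot simply be added, because Week 16 pre-dose heart rate enters them with opposite signs. Take SD 10, within-visit ρ = 0.82 (change SD 10 × √0.36 = 6) and ρ = 0.68 between Day 1 and either Week 16 reading (change SD 10 × √0.64 = 8). The covariance is 82 − 68 − 100 + 68 = −18. The SD from Day 1 is √(36 + 64 − 36) = 8 bpm.

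**6. Percent change.** Here the Day 1 value is also the denominator, so the displacement is not a constant that can be read off the pre-dose point.

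**The case against.** The strongest reply is that little is lost. Appendix 1.D is labelled exploratory, and its plots carry no test, threshold or decision. The raw beats/min overlay in the same item shows the Week 16 course without any baseline. SAP 9.E reports extension vital signs from both baselines, and gives Week 16 pre-dose values and change. Protocol 11.9 names the double-blind baseline as one of two references for extension safety data, so its use here breaks no stated rule. Neither SAP 5.B nor Protocol 11.9 assigns the OLE baseline to these particular plots. All of this stands, and it limits the consequence.

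A reader might infer that the wrong reference could conceal the Week 16 heart-rate fall or remove it from the report. The documents do not support that. The absolute-change curve moves vertically, so the drop from a drawn pre-dose point survives, and the same-visit effect appears in the safety tables. A reader might also add variances and conclude that the plotted SD grows from 6 to √(6² + 8²) = 10 bpm. That assumes zero covariance, which is normally negative, and the worked example gives 8.

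Some related text is blacked out, including Protocol 10.5.7.4, parts of the SAP sections after vital signs and two items of Appendix 1.D. Handling that bears on this may sit there.

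The reply does not make the change plots right. A reader can subtract the mean offset from the absolute curve if the pre-dose point is shown, but cannot recover the SD or exactly correct the percent-change curve.

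**Conclusion.** The point holds for two displays, the Week 16 absolute-change and percent-change heart-rate overlays. Followed as written, they use a reference about 16 weeks old and combine the acute effect with the between-visit pre-dose difference. That difference cannot be sized from the documents. Under the assumed SD of 6 to 10 bpm and 20 to 30 subjects per former arm, chance alone displaces a mean absolute-change curve by about ±2.2 to ±4.4 bpm. The SD will usually be wider, by an amount that depends on correlations the documents do not report. The text supports the wording problem firmly. The numerical impact rests on assumption. This is a small correction to an exploratory safety display and does not touch the trial's conclusions.

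**What to change.** In SAP Appendix 1.D, limit the opening rule. Keep DB Baseline for the EASI and Day 1 items. For the Week 16 heart-rate absolute-change and percent-change overlays, state that Baseline means the Week 16 pre-dose (OLE) baseline and that nominal time is counted from the Week 16 dose. A DB-baseline version may stay as a second display.

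The amendment should also settle which pre-dose reading is used. SAP 5.B takes the lowest pre-dose heart rate under the double-blind baseline but the last pre-dose measurement for the OLE baseline. Importing the OLE definition unchanged would give the paired Day 1 and Week 16 plots different comparators, so one rule (lowest or last) should be named for both.

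The cost is a sentence or two in the appendix and a small programming change. The Week 16 pre-dose heart rate is already collected, and the OLE baseline is already needed for the vital-sign tables.
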